## 15.7 Reporting and Exclusions

All patients included in the study must be assessed for safety, tolerability, and response to treatment, even if there are major protocol treatment deviations or if they are ineligible. Each patient will be assigned one of the following categories: 1) complete response, 2) partial response, 3) stable disease, 4) progressive disease, 5) early death from malignant disease, 6) early death from toxicity, 7) early death because of other cause, or 9) unknown (not assessable, insufficient data).

All of the patients who met the eligibility criteria and received study drugs for 4 weeks should be included in the main analysis of the clinical benefit rate. Patients in response categories 4-9 should be considered to have a treatment failure (disease progression). Thus, an incorrect treatment schedule or drug administration does not result in exclusion from the analysis of the response and clinical benefit rate.

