## 6.9 Criteria for Removal from Study

Patients will be removed from study when any of the criteria listed below apply. All patients who initiate protocol treatment will be included in the overall evaluation of response (intent-to-treat analysis). All reasons for discontinuation of therapy should be documented clearly in the medical record.

If a subject discontinues or withdraws from the study, every attempt will be made to get a tissue/tumor biopsy at the end of treatment, along with blood if the subject is able and willing to do so.

Patients may be withdrawn from the study if they experience any of the following:

- Disease progression, per investigator assessment
- Intolerable toxicity to taselisib or enzalutamide. Patients experiencing toxicity to taselisib or enzalutamide can continue on study with single agent enzalutamide or taselisib, respectively, at the discretion of the treating physician. Patients will be followed for disease progression and should continue radiologic assessments every 2 cycles as per the study.

Other reasons for patient discontinuation may include, but are not limited to, the following:

- Non-compliance with the study protocol, including, but not limited to not attending the majority of scheduled visits. The Protocol Chair will determine when non-compliance should lead to removal from study. Note: The patients will still be included in the overall evaluation of response (intent-to-treat analysis).
- Patient personal decision. The reason for discontinuation from the study must be documented. The patients will be included in the overall evaluation of response (intent-to-treat analysis) if any protocol therapy was administered prior to withdrawal.
- If the patient becomes pregnant
- Patient is lost to follow-up
- Study is terminated for any reason

The investigator has the right to discontinue a patient from the study for any medical condition that the investigator determines may jeopardize the patient’s safety if he or she continues in the study; for reasons of noncompliance (e.g., missed doses, visits); or if the investigator determines it is in the best interest of the patient. The Protocol Chair should be notified in such cases.

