#### 10.1.2 Evaluable for objective response:

Only those patients who have evaluable disease present at baseline, have received at least one cycle of therapy, and have had their disease re-evaluated will be considered evaluable for response. These patients will have their response classified according to the definitions stated below. (Note: Patients who exhibit objective disease progression prior to the end of cycle 1 will also be considered evaluable.)

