### 15.3 Phase II Study

The primary endpoint of the phase II portion is to assess the CBR of enzalutamide + taselisib at 16 weeks. This will be studied using a Simon two-stage design. Because there is sparse data on single agent enzalutamide, we also plan to accrue patients to a single agent enzalutamide arm. Patients will be randomized to the dual therapy vs monotherapy arms using a 3:1 randomization. The coordinating center (VICC) will randomly assign patients to an arm. No direct comparison of the two arms will be conducted. Rather, the monotherapy arm will serve as an informal anchor when interpreting results, and will be especially informative when interpreting many of the secondary analyses.

We have designed the enzalutamide + taselisib arm as a Simon optimal two stage. This design allows for early termination for inefficacy. The antiandrogen bicalutamide, in a prior study with a similar patient population, resulted a CBR of approximately 20%. Thus, for this study, we aim to show an improvement in CBR from 20% to 40%. With a Type I error of 10% and a Type II error of 10%, we will accrue 17 patients in the first stage. After the first 17 patients in the phase II portion have completed 2 cycles and obtained scans, the data will be analyzed. If 4 out of the 17 have a response (CR, PR, or SD), we will expand the study to a total of 37. If, at the end of the trial, there are 11 out of 37 patients with response, we will deem the regimen worthy of further study. If there are 3 or few responses in the first 17 patients, the study will terminate early. If 10 or few responses are seen in the total of 37, the regimen will be deemed unworthy of further study. This study has a 55% probability of stopping early under the null hypothesis. Patients whose disease progresses within 30 days of starting the study without a DLT will be replaced during the phase I portion.

Concurrently, an arm of single agent enzalutimide will be accrued. For every 3 patients randomized to the enzalutamide + taselisib arm, 1 patient will be randomized to the enzalutamide only arm. If the dual therapy arm terminates early due to inefficacy, we will also terminate the monotherapy arm. Thus, this arm will have a minimum of 6 and a maximum of 12 patients. We do not plan to do any formal analysis on this group of patients.

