### 15.4 Sample Size

Based on preliminary data on these therapies, we expect to require 15 patients for the Phase Ib portion of the trial. However, with 4 dose levels it is possible, though not likely that 24 patients will be required. For the phase II portion of the trial, we will require  $17+6=23$  to  $37+12=49$  (23-59) patients depending on whether the number of responses reach the threshold at the interim analysis. Patients in the phase I portion who are the recommended dose for phase II will be included in the evaluable patients for phase II. The total sample size for the study will be approximately 73 patients.

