## 15.5 Reporting

Demographic information such as age and race will be tabulated. Descriptive statistics, including means, medians, standard deviations, and ranges for continuous parameters, as well as percents and frequencies for categorical parameters, will be presented. Investigation for outliers and assumptions for statistical analysis, e.g., normality and homoscedasticity will be made. Adverse medical events will be tabulated. NCI toxicity Grade 3 and Grade 4 laboratory abnormalities will be listed.

All patients who receive any study drugs will be included in the toxicity evaluation. All patients who receive study drugs for at least 4 weeks will be included in the efficacy evaluation (modified intention to treat). Deaths, early progression, and other reasons for drop-out of the study prior to 4 weeks will be reported.

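### The main CBR analysis leaves out patients with less than 4 weeks of study drugs, Section 6.9 counts everyone who starts treatment, and the plan does not say which rule prevails

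*Combined protocol and SAP*

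**What the plan says.** Four places in the combined protocol and SAP define who counts for response or CBR.

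- Section 15.7: "All of the patients who met the eligibility criteria and received study drugs for 4 weeks should be included in the main analysis" of the CBR. The same section adds: "Patients in response categories 4-9 should be considered to have a treatment failure (disease progression"; those categories run from progressive disease through early death to unknown.
- Section 15.5: "All patients who receive study drugs for at least 4 weeks will be included in the efficacy evaluation (modified intention to treat"). Its next sentence says that deaths, progressions and other drop-outs before 4 weeks will be reported.
- Section 6.9: "All patients who initiate protocol treatment will be included in the overall evaluation of response (intent-to-treat analysis"). It repeats this for non-compliant patients and for patients who withdraw after receiving any protocol therapy.
- Section 10.1.2 requires at least one cycle and a re-evaluation, but a note adds: "Patients who exhibit objective disease progression prior to the end of cycle 1 will also be considered evaluable".

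Three statements bear on who fills the places in the two-stage design.

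- Section 15.3, interim look: "After the first 17 patients in the phase II portion have completed 2 cycles and obtained scans, the data will be analyzed".
- Section 15.3, replacement: "Patients whose disease progresses within 30 days of starting the study without a DLT will be replaced during the phase I portion". No sentence addresses replacement in phase II.
- Section 15.4: "Patients in the phase I portion who are the recommended dose for phase II will be included in the evaluable patients for phase II". Under Section 6.2.2, early progressors in that portion were replaced.

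**The concern.** A patient who starts treatment and dies on day 20 is a failure under 6.9 and absent under 15.5 and 15.7. A patient with documented progression in week 3 is evaluable under the note in 10.1.2 and also absent under 15.5 and 15.7. Nothing says which rule governs, so the denominator could be chosen after the results are known.

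The exclusion is not neutral. CBR needs CR, PR or stable disease for at least 16 weeks. A patient who progresses or dies before week 4 cannot reach that. One who drops out that early, before any scheduled scan, would have no assessment to support it and would fall into the unknown category, which 15.7 scores as failure. Removing such patients can only push the reported rate up.

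The decision rule is a count: at least 4 of 17 to continue, at least 11 of 37 to call the regimen worthy of further study. Whether an excluded patient still occupies one of those places therefore matters, and the plan does not say.

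**Working it through.** **Inputs.** From Section 15.3: null CBR 20%, target 40%, type I and type II error 10% each; stop at 3 or fewer of 17; positive at 11 or more of 37; 55% probability of early stopping under the null. Assumption: d is the share of treated combination patients who stop before 4 weeks without benefit. The documents give no value, so 1%, 2% and 5% are shown.

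**Step 1: reproduce the design.** With p the CBR among counted patients:

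- P(stop early) = P(Bin(17, p) ≤ 3)
- P(go) = Σ over x = 4 to 17 of P(Bin(17, p) = x) × P(Bin(20, p) ≥ 11 − x)

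At p = 0.20, P(stop early) = 0.549 (the plan says 55%) and P(go) = 0.0948. At p = 0.40, P(go) = 0.903. The design is as stated, with a margin of about half a percentage point below the 10% limit.

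**Step 2: early stops dropped and not replaced.** The dropped patients are all non-benefit cases, so the number of patients with benefit is unchanged. Against the fixed thresholds, P(go) stays at 0.095. Only the reported rate moves, to about 0.20/(1 − d):

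- d = 2%: 0.20/0.98 = 20.4%
- d = 5%: 0.20/0.95 = 21.1%

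The shift is 0.4 to 1.1 percentage points. The standard error at n = 37 is √(0.20 × 0.80/37) = 6.6 points. As a single-trial example, 10/37 = 27.0% would be shown as 10/35 = 28.6% if two patients were dropped.

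**Step 3: early stops dropped and their places refilled.** The 17 and 37 then consist only of patients who passed 4 weeks. If the all-treated CBR is 20%, each counted patient has CBR 0.20/(1 − d), and the formulas in Step 1 give:

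| d | CBR among counted | P(stop early) | P(go) |
|---|---|---|---|
| 0 | 0.200 | 0.549 | 0.095 |
| 1% | 0.202 | 0.540 | 0.100 |
| 2% | 0.204 | 0.532 | 0.106 |
| 5% | 0.211 | 0.505 | 0.125 |

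P(go) reaches 0.10 at d of about 0.95%.

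**Step 4: is refilling in the plan?** It is not stated for phase II; the replacement sentence in 15.3 is confined to phase I. Two statements keep it open. The interim look is tied to the first 17 who have completed 2 cycles and had scans, which an early stopper cannot do. The pooling in 15.4 can bring in phase Ib patients from a set in which early progressors had been replaced.

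**Step 5: how large might d be?** The first on-treatment scan comes after 2 cycles, at about week 8, so radiological progression before week 4 will seldom be recorded. That points to a small d for progression. The documents do not quantify deaths or drop-outs before week 4.

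**The case against.** The strongest defence is that the 4-week set is deliberate. Sections 15.5 and 15.7 agree, both are statistical sections, 15.5 labels the set as modified intention to treat, and only 15.7 names the main CBR analysis; 6.9 is about removal from study. Since the lead-in, a patient lost in cycle 1 has had no taselisib, so counting that patient as a combination failure is one estimand among several. These points stand as far as they go. They show intent, but they do not reconcile 6.9, and they do not make the exclusion neutral. Nor does the 4-week rule secure exposure to the combination: taselisib starts on day 1 of cycle 2, so 4 weeks can be met on enzalutamide alone.

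Some stronger readings are tempting, and the documents do not support them.

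- *The trial's type I error exceeds 10%.* This needs three things: refilled phase II places, a non-zero early-loss share, and a 20% null that refers to all treated patients. Section 15.3 provides for no refilling in phase II and gives the bicalutamide figure without a denominator. If the 20% refers to a 4-week set, the rate stays at 0.095.
- *Section 15.7 contradicts its own failure rule.* The rule can operate within the 4-week set, on progression, death or unknown status after week 4.
- *Section 10.1.2 is opposed to 15.7 throughout.* It also asks for one cycle; only its note on progression in cycle 1 differs.
- *Grade 3 or 4 rash with fever in 7 of 8 combination patients (7.2.1.3) implies heavy early loss.* Those cases came before the lead-in. Patients treated since then receive no taselisib in the first 4 weeks, so taselisib rash cannot remove them in that window. For the earlier patients, the documents do not say whether any stopped all study drug before 4 weeks.
- *Early losses would be hidden.* Section 15.5 already plans to report them.

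**Conclusion.** The conflict between 6.9 and Sections 15.5 and 15.7 is real and unresolved, with a narrower one through the note in 10.1.2. Following the 4-week rule biases the reported CBR in one direction, upward. The size is probably small: 0.4 to 1.1 points on a true 20% for assumed early losses of 2% to 5%.

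The operating characteristics are affected only if phase II places are refilled. In that case, and on an all-treated reading of the null, the rate of 0.095 becomes 0.100, 0.106 and 0.125 at losses of 1%, 2% and 5%. These are conditional figures; they do not show a defect in the Simon boundaries, which reproduce exactly. The change is still worth making because the design has little slack and the ambiguity can be removed before analysis at almost no cost.

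**What to change.** - **15.5 and 15.7:** replace the 4-week condition with: *The main CBR analysis includes all eligible combination-arm patients who start protocol treatment; progression, death or drop-out before 4 weeks counts as no clinical benefit.*
- **6.9 and 10.1.2:** align both with that wording, so that one definition applies throughout.
- **15.3:** add: *The 17 and 37 are the first such patients to start treatment. No phase II patient is replaced. The interim analysis takes place when each of the 17 has had the 2-cycle scan or has stopped earlier.*
- **15.4:** apply the same counting rule to phase Ib patients pooled into phase II.
- Keep CBR in the 4-week set, or in patients who took at least one taselisib dose, as a supporting estimate.

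The cost is wording only; sample size and thresholds do not change. With these patients counted as failures, the design keeps its calculated properties on the all-treated scale (0.095 at 20%, 0.903 at 40%). There are two downsides. The observed CBR will be slightly lower, for example 11/37 = 29.7% instead of 11/35 = 31.4% if two patients stop early. After the lead-in, some counted failures will never have received taselisib, which is why the supporting estimate is worth keeping.
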